
Inclusion Criteria for Cohort 3 Observation Period
 
Individuals eligible to participate in this study must meet all of the following criteria:
 
 1. Parent(s) or guardian(s) willing and able to provide signed informed consent after the nature of the study has been explained and prior to performance of any research-related procedure. 		

NAME OF COMPANY	SUMMARY TABLE	FOR NATIONAL AUTHORITY USE ONLY:
BioMarin Pharmaceutical Inc. [name] [name]	Referring to Part of the Dossier: Volume: Page:	
NAME OF FINISHED PRODUCT: BMN 111		
NAME OF ACTIVE INGREDIENT: Modified rhCNP	Reference:	

Also, willing and able to provide written assent (if applicable) after the nature of the study has been explained and prior to performance of any research-related procedure.
 
 2. Birth to \leq 3 months of age at study entry. 3. Have ACH, documented by genetic testing 4. Are willing and able to perform all study procedures as physically possible 
After completing observation period subjects must fulfill the general eligibility criteria prior to receiving treatment with study drug.
		

Exclusion Criteria for Cohort 3 Observation Period
 
Individuals who meet any of the following exclusion criteria are not eligible to participate in the study:
 
 1. Have hypochondroplasia or short stature condition other than ACH (e.g., trisomy 21, pseudoachondroplasia) 2. Have any of the following disorders: 
 • Hypothyroidism • Insulin-requiring diabetes mellitus • Autoimmune inflammatory disease (including celiac disease, lupus (SLE), juvenile dermatomyositis, scleroderma, and others) • Inflammatory bowel disease • Autonomic neuropathy 3. Have an unstable clinical condition likely to lead to intervention during the course of the study, including progressive cervical medullary compression 4. Have a history of any of the following: 
 • Renal insufficiency • Anemia 5. Have a history of cardiac or vascular disease, including the following: 
 • Cardiac dysfunction • Hypertrophic cardiomyopathy • Congenital heart disease • Cerebrovascular disease, aortic insufficiency • Clinically significant atrial or ventricular arrhythmias 6. Current treatment with antihypertensive medications, ACE inhibitors, angiotensin II receptor blockers, diuretics, beta-blockers, calcium-channel blockers, cardiac glycosides, systemic anticholinergic agents, any medication that may impair or enhance compensatory tachycardia, drugs known to alter renal function that is expected to continue for the duration of the study 		

NAME OF COMPANY BioMarin Pharmaceutical Inc. [name] [name]	SUMMARY TABLE Referring to Part of the Dossier: Volume: Page:	FOR NATIONAL AUTHORITY USE ONLY:
NAME OF FINISHED PRODUCT: BMN 111		
NAME OF ACTIVE INGREDIENT: Modified rhCNP	Reference:	

7. Have had regular long-term treatment (> 1 month) with oral corticosteroids (low-dose ongoing inhaled steroid for asthma is acceptable) in the previous 3 months
 
8. Concomitant medication that prolongs the QT/QTc interval within 14 days or 5 half-lives, whichever is longer, before the Screening visit
 
9. Have used any other investigational product or investigational medical device for the treatment of ACH or short stature
 
10. Planned or expected bone-related surgery (ie. surgery involving disruption of bone cortex), during the study period.
 
11. Planned or expected to have limb-lengthening surgery during the study period.
 
12. Have any condition that, in the view of the Investigator, places the subject at high risk of poor compliance with the visit schedule or of not completing the study.
 
13. Concurrent disease or condition that, in the view of the Investigator, would interfere with study participation
		

After completing observation period subjects must fulfill the general eligibility criteria prior to receiving treatment with study drug.
		

INVESTIGATIONAL PRODUCT, DOSE, ROUTE, and REGIMEN: The clinical drug product will be supplied in sterile, single-dose, Type I glass vials with coated stopper and flip-off aluminum cap. BMN 111 drug product is supplied as a 0.8-mg or 2-mg lyophilized, preservative-free, white-to-yellow powder for reconstitution with sterile water for injection (WFI). The reconstituted solution is colorless to yellow and contains 0.8 mg/mL to 2 mg/mL of BMN 111, as well as citric acid, sodium citrate, trehalose, mannitol, methionine, polysorbate 80, and sterile WFI. The target pH of the reconstituted solution is 5.5. Sterile WFI will be commercially sourced. All reconstitution and dose preparation steps will be performed as indicated in the BMN 111 Injection Guide and Injection video.
 
BMN 111 will be administered as a single SC injection given daily at approximately the same time each day whenever possible. Following administration of each dose at clinic visits, subjects should be observed for 8 hours after the injection on Days 1 and 2; 4 hours on Days 3 and 8; and 1 hour on subsequent dosing visits. Subjects should be observed for 30 minutes after every injection that is not administered at the clinic.
		

REFERENCE THERAPY, DOSE, ROUTE, and REGIMEN: BMN 111-placebo lyophilized product will be supplied in sterile, single-dose, Type I glass vials with coated stopper and flip-off aluminum cap. The placebo is designed to be comparable in appearance to the drug product and contains all of the components of the drug product except the drug substance.
 
All reconstitution and dose preparation steps should be performed as indicated in the Study Drug Injection Guide and Injection instruction media.
		

NAME OF COMPANY	SUMMARY TABLE	FOR NATIONAL AUTHORITY USE ONLY:
BioMarin Pharmaceutical Inc. [name] [name]	Referring to Part of the Dossier: Volume: Page:	
NAME OF FINISHED PRODUCT: BMN 111		
NAME OF ACTIVE INGREDIENT: Modified rhCNP	Reference:	
Placebo will be administered as a single SC injection given daily at approximately the same time each day whenever possible. Following administration of each dose at clinic visits, subjects should be observed for 8 hours after the injection on Days 1 and 2; 4 hours on Days 3 and 8; and 1 hour on subsequent dosing visits. Subjects should be observed for 30 minutes after every injection that is not administered at the clinic.		
DURATION OF TREATMENT: 52 weeks		
CRITERIA FOR EVALUATION:		

Safety: The following safety outcome measurements will be assessed:
 
 • Incidence of AEs and SAEs • Imaging assessments (X-rays of the spine and entire lower extremities, DXA of total body less head and spine) • CBCL • Vital signs (heart rate, blood pressure, respiratory rate, and temperature) • Physical examination (including neurological assessment) • Hip clinical assessment • Laboratory test results (urinalysis, chemistry, hematology) • Electrocardiogram (ECG) • Echocardiogram • Anti-BMN 111 immunogenicity assessments • Cortisol levels • Prolactin levels 		

Primary Efficacy: The following efficacy outcome measurements will be assessed:
 
 • Safety and tolerability of BMN 111 in children age 0 to < 60 months with ACH • Change from baseline in length/height Z-score 		

Secondary Efficacy:
 
The following measurements will be assessed:
 
 • Change from baseline in AGV • Change from baseline in upper:lower body segment ratio • MRI to define skull and brain morphology (including dimensions of foramen magnum, ventricular and brain parenchymal dimensions) • Sleep study • Changes in bone and collagen metabolism and BMN 111 pharmacodynamic biomarkers 		

Clinical outcome assessments:
 
 • Bayley-III • Wee-FIM 		

NAME OF COMPANY BioMarin Pharmaceutical Inc. [name] [name]	SUMMARY TABLE Referring to Part of the Dossier: Volume: Page:	FOR NATIONAL AUTHORITY USE ONLY:
NAME OF FINISHED PRODUCT: BMN 111		
NAME OF ACTIVE INGREDIENT: Modified rhCNP	Reference:	

 ITQOL 
Pharmacokinetics: PK sampling will be carried out over the entire study period in sentinel subjects and subjects randomized to BMN 111 or placebo. Whenever possible, the following PK parameters for sentinel subjects and subjects randomized to BMN 111 will be estimated by non-compartmental analysis:
 
 Area under the plasma concentration-time curve from time 0 to infinity (AUC_{0-∞}) Area under the plasma concentration-time curve from time 0 to the time of last measurable concentration (AUC_{0-t}) Maximum observed plasma concentration (C_{max}) Time to reach C_{max} (T_{max}) Elimination half-life (t_{1/2}) Apparent clearance (CL/F) Apparent volume of distribution (V_d/F) 
Exploratory: The following exploratory measurements will be assessed:
 
 Clinical photography (optional) Optional evaluation of genomic biomarkers 		

STATISTICAL METHODS:
 
Sample Size Determination:
 
Approximately 70 subjects age 0 to < 60 months at study entry will participate in this study. No formal sample size calculations were performed. The number of subjects is considered appropriate to evaluate the safety and efficacy of BMN 111 in the target population.
 
Safety Analysis:
 
All AEs will be coded using the most current version of Medical Dictionary for Regulatory Activities (MedDRA) to assign system organ class and preferred term classification to event and disease, based on the original terms entered on the eCRF. The incidence of AEs will be summarized by system organ class, preferred term, relationship to study treatment as assessed by the investigator, seriousness, and severity. All AEs, including SAEs and AEs that lead to permanent discontinuation from the study and from the study treatment, will be listed.
 
All other safety measures including laboratory tests, vital signs, ECG, echocardiogram, hip clinical assessment, and concomitant medication data will also be summarized descriptively. Data summaries will be presented by treatment group (when applicable) for each cohort and overall. All safety results will be listed.
		

NAME OF COMPANY BioMarin Pharmaceutical Inc. [name] [name]	SUMMARY TABLE Referring to Part of the Dossier: Volume: Page:	FOR NATIONAL AUTHORITY USE ONLY:
NAME OF FINISHED PRODUCT: BMN 111		
NAME OF ACTIVE INGREDIENT: Modified rhCNP	Reference:	
Efficacy Analysis: Efficacy variables, including AGV (based on length/height) and length/height Z-score according to normal reference standards (not ACH), along with their change from baseline will be summarized by treatment group and cohort. Comparisons between treatment groups by cohort on these variables will be carried out where appropriate. Statistical comparisons will be considered descriptive. 95% CIs will be provided along with p values for treatment group comparisons. Sentinel subjects will be summarized apart for both efficacy and safety.		
Pharmacokinetic Analysis: PK parameters generated over the course of the study will be evaluated and summarized with descriptive statistical measures (mean, standard deviation, coefficient of variation [CV%], minimum, median and maximum). Correlative analyses of some of the PK parameters with efficacy, safety and immunogenicity measures may be conducted.		
HRQoL and Functional Independence: For the Health-Related Quality of Life (HRQoL) and functional independence assessments, individual items, domain, and summary scores generated over the course of the study will be evaluated with descriptive statistical measures (mean, standard deviation, minimum, median, and maximum) as well as displayed visually.		

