NAME OF COMPANY BioMarin Pharmaceutical Inc. [name] [name]	SUMMARY TABLE Referring to Part of the Dossier: Volume: Page:	FOR NATIONAL AUTHORITY USE ONLY:
NAME OF FINISHED PRODUCT: BMN 111		
NAME OF ACTIVE INGREDIENT: Modified rhCNP	Reference:	

Analysis of safety data from the 6 month initial phase of Study 111-202 showed that treatment with BMN 111 for 6 months at the doses of 2.5, 7.5, 15, and 30 µg/kg was generally well tolerated (refer to current Investigator's Brochure for specific details). One subject (30 µg/kg) in 111-202 withdrew due to an AE. The subject developed non-serious, asymptomatic Grade 1 intermittent Wolff-Parkinson-White pattern, which was discovered on a routine day 10-study monitoring ECG. The most common AEs across all cohorts were injection site reactions, asymptomatic hypotension, headache, and nasopharyngitis. Based on previous experience of the ongoing Phase 2 clinical trial, including the 24 month data cut at 15 µg/kg, injection site reactions have been identified as risks associated with BMN 111 injections. The majority of hypotension events were grade 1 and reported in the setting of routine BP measurement. All reported events of hypotension were transient and resolved without medical intervention. For a detailed summary of risks, please refer to the current version of the Investigator's Brochure supplied by BioMarin.
 
Analysis of efficacy data from the 6 month initial phase of Study 111-202 showed that subjects treated with BMN 111 for 6 months at doses ranging from 2.5 to 15 µg/kg daily had a dose-dependent improvement in AGV, with ~50% improvement in AGV seen at the 15 µg/kg dose. The data from Cohort 4 (30 µg/kg) show an apparent greater than dose-proportional increase in BMN 111 plasma exposure (C_{max} and AUC_{0-t}), with a marginal improvement in both absolute AGV and change from baseline AGV after 6 months of BMN 111 treatment when compared with Cohort 3 (15 µg/kg).
 
Study 111-206 is a Phase 2 randomized, double-blind, placebo-controlled clinical trial of BMN 111 in infants and younger children with a diagnosis of ACH who are 0 to < 60 months old. This 52-week study will enable assessment of BMN 111 efficacy and safety, tolerability, pharmacodynamics biomarkers, and PK in this population. Additional exploratory endpoints pertaining to medical complications of ACH will also be evaluated.
 
Efficacy/toxicity studies have been conducted in neonatal and very young animals (7 day postpartum mouse and rat) in both a disease (TD mouse) and non-disease (rat) model. Given that this is the first study in infants and young children, an age based cohort study design is used to assess safety and PK in young children (Cohort 1, ≥ 24 to < 60 months) prior to dosing toddlers (Cohort 2, ≥ 6 to < 24 months) and infants (Cohort 3, 0 to < 6 months). PK will be monitored and evaluated; Day 1 PK data from the sentinel subjects will inform dose selection modification for the sentinel subjects and for the rest of the cohort to target the observed exposure of the 15 µg/kg dose group in Study 111-202. Safety, efficacy and PK data from Study 111-202, a Phase 2 study in children with ACH, where a dose of 15 µg/kg has been and continues to be studied, are expected to be the most relevant, and translatable to this study (111-206).
		

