
Data Monitoring Committee (DMC)
 
In addition to safety and PK monitoring by BioMarin personnel, an independent DMC will act as an advisory body to BioMarin and will monitor the safety and PK of subjects in the study. After the sentinel subjects complete 12 weeks of dosing, a DMC review will occur to evaluate all available safety and PK data. Upon approval by the DMC, the next younger cohort will be opened and the 3 sentinel subjects will be enrolled.
 
The DMC will make recommendations for stopping or continuing the study on an individual subject level and/or on a cohort level per the pre-specified stopping criteria. Based on criteria outlined in the protocol, the DMC may also make endorsements for dose adjustments if needed.
 
Please see DMC Charter for further details.
 
Individual Subject Stopping Criteria
 
For individual subjects treated with BMN 111, DMC will be informed if any of the following individual subject stopping criteria should occur. Temporary dosing suspension, permanent discontinuation of dosing, or dose reduction for the individual subject will be considered.
 
 • Any treatment-emergent adverse event (AE) assessed as at least Grade 4 by the Investigator and/or Sponsor Medical Monitor • Any treatment-emergent AE of at least Grade 3 assessed as related to study drug by the Investigator and/or Sponsor Medical Monitor • Any two treatment-emergent Grade 2 symptomatic hypotension events within 7 days (non-urgent medical intervention indicated) or any Grade 3 hypotensive event (urgent medical intervention or hospitalization indicated) assessed by the Investigator and/or Sponsor's Medical Monitor 		

NAME OF COMPANY BioMarin Pharmaceutical Inc. [name] [name]	SUMMARY TABLE Referring to Part of the Dossier: Volume: Page:	FOR NATIONAL AUTHORITY USE ONLY:
NAME OF FINISHED PRODUCT: BMN 111		
NAME OF ACTIVE INGREDIENT: Modified rhCNP	Reference:	

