
 • Clinically significant finding or arrhythmia on ECG that indicates abnormal cardiac function or conduction or prolongation of QTc-F >500 msec • Clinically significant new or worsening signs of cervicomedullary compression as determined by the Investigator and in consultation with Sponsor medical monitor and neurosurgical specialist (if needed) • Adverse findings on clinical hip exam or hip imaging assessments that are determined to be clinically significant as determined by the Investigator and in consultation with Sponsor Medical Monitor and orthopedic specialist (if needed) 		

If the subject meets any stopping criterion, after Investigator consultation with the BioMarin Medical Monitor and DMC, the subject may be re-challenged at the same dose. If the subject meets stopping criteria on re-challenge or if re-challenge is not clinically indicated, other options that may be considered include:
 
 • Re-challenge at lower dose with consideration given to upward titration to tolerated dose • Permanent treatment discontinuation (with an option of ongoing assessment in the study) 		

Cohort Stopping Criteria
 
For each cohort, a DMC review will be conducted if any of the following cohort stopping criteria occur in subjects treated with BMN 111. Temporary dosing suspension, permanent discontinuation of dosing, or dose reduction for the cohort(s) will be considered and the impact on all other age cohorts will be assessed.
 
 • Any treatment-emergent AE assessed as at least Grade 4 by the Investigator and/or Sponsor Medical Monitor • Any two subjects have a treatment-emergent AE of at least Grade 3 assessed as related to study drug by the Investigator and/or Sponsor Medical Monitor • Any two subjects have two treatment-emergent Grade 2 symptomatic hypotension events within 7 days (non-urgent medical intervention indicated) or any two subjects cohort have a Grade 3 hypotensive event (urgent medical intervention or hospitalization indicated) assessed by the Investigator and/or Sponsor's Medical Monitor • Any two subjects have a clinically significant finding or arrhythmia on ECG that indicates abnormal cardiac function or conduction or prolongation of QTc-F >500 msec 		

NAME OF COMPANY BioMarin Pharmaceutical Inc. [name] [name]	SUMMARY TABLE Referring to Part of the Dossier: Volume: Page:	FOR NATIONAL AUTHORITY USE ONLY:

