9.1.2 Stopping Criteria

Individual Subject Stopping Criteria

For individual subjects treated with BMN 111, DMC will be informed if any of the following individual subject stopping criteria should occur. Temporary dosing suspension, permanent discontinuation of dosing, or dose reduction for the individual subject will be considered.

- Any treatment-emergent adverse event (AE) assessed as at least Grade 4 by the Investigator and/or Sponsor Medical Monitor
- Any treatment-emergent AE of at least Grade 3 assessed as related to study drug by the Investigator and/or Sponsor Medical Monitor
- Any two treatment-emergent Grade 2 symptomatic hypotension events within 7 days (non-urgent medical intervention indicated) or any Grade 3 hypotensive event (urgent medical intervention or hospitalization indicated) assessed by the Investigator and/or Sponsor's Medical Monitor

- Clinically significant finding or arrhythmia on electrocardiogram (ECG) that indicates abnormal cardiac function or conduction or prolongation of QTc-F > 500 msec
- Clinically significant new or worsening signs of cervicomedullary compression as determined by the Investigator and in consultation with Sponsor medical monitor and neurosurgical specialist (if needed)
- Adverse findings on clinical hip exam or hip imaging assessments that are determined to be clinically significant as determined by the Investigator and in consultation with Sponsor Medical Monitor and orthopedic specialist (if needed)

If the subject meets any stopping criterion, after Investigator consultation with the BioMarin Medical Monitor and DMC, the subject may be re-challenged at the same dose. If the subject meets stopping criteria on re-challenge or if re-challenge at same dose is not clinically indicated, other options that may be considered include:

- Re-challenge at lower dose with consideration given to upward titration to tolerated dose
- Permanent treatment discontinuation (with an option of ongoing assessment in the study)

Cohort Stopping Criteria

For each cohort, a DMC review will be conducted if any of the following cohort stopping criteria occur in subjects treated with BMN 111. Temporary dosing suspension, permanent discontinuation of dosing, or dose reduction for the cohort(s) will be considered and the impact on all other age cohorts will be assessed.

- Any treatment-emergent AE assessed as at least Grade 4 by the Investigator and/or Sponsor Medical Monitor

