- Any two subjects have a treatment-emergent AE of at least Grade 3 assessed as related to study drug by the Investigator and/or Sponsor Medical Monitor
- Any two subjects have two treatment-emergent Grade 2 symptomatic hypotension events within 7 days (non-urgent medical intervention indicated) or any two subjects cohort have a Grade 3 hypotensive event (urgent medical intervention or hospitalization indicated) assessed by the Investigator and/or Sponsor's Medical Monitor
- Any two subjects have a clinically significant finding or arrhythmia on ECG that indicates abnormal cardiac function or conduction or prolongation of QTc-F > 500 msec

- Any two subjects have adverse findings on clinical hip exam or hip imaging assessments that are determined to be clinically significant as decided by principal investigator and in consultation with Sponsor medical monitor and orthopedic specialist (if needed)

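### The cohort hypotension rule counts two children within each branch separately, so one child with repeated Grade 2 events plus one with a Grade 3 event triggers no prescribed cohort DMC review

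*Protocol*

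**What the plan says.** At the level of the single child, the protocol treats two patterns as alternatives (Synopsis and Section 9.1.2, Individual Subject Stopping Criteria): "Any two treatment-emergent Grade 2 symptomatic hypotension events within 7 days (non-urgent medical intervention indicated) or any Grade 3 hypotensive event". Either one qualifies the child. The consequence is that "DMC will be informed if any of the following individual subject stopping criteria should occur", and action is considered for that child.

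At cohort level, "For each cohort, a DMC review will be conducted if any of the following cohort stopping criteria occur in subjects treated with BMN 111". Suspension, discontinuation or dose reduction is then considered for the cohort, and the impact on the other age cohorts is assessed. The hypotension bullet opens with a count of two children for the Grade 2 pattern and then gives the count afresh for the Grade 3 branch: "events within 7 days (non-urgent medical intervention indicated) or any two subjects cohort have a Grade 3 hypotensive event". The wording is the same in the Synopsis and in Section 9.1.2.

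The other cohort criteria are:

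- any adverse event of Grade 4 or higher;
- two children with a drug-related event of Grade 3 or higher;
- two children with significant ECG findings;
- two children with significant hip findings.

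**The concern.** The cohort bullet requires two children in each branch and nowhere lets one child from each branch make up the two. A mixed pair has one child with the repeated Grade 2 pattern and one with a Grade 3 event that needs urgent intervention or hospitalization. It is at least as severe as two children with the Grade 2 pattern, yet only the milder pair prompts the cohort review.

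Hemodynamic change is named as a possible acute dose-limiting effect (Section 7.5.1). This is the first experience in the age group, and the protocol accepts that exposure may exceed the target (Section 9.1.1). A cohort's dose, adjusted or not, becomes the starting dose for the next younger sentinels (Section 9.1). The step at stake is the one in which the dose of the whole cohort, and its consequences for the other cohorts, must be considered.

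**Working it through.** **Logic.** Let A be a child with two Grade 2 symptomatic hypotension events within 7 days, and B a child with one Grade 3 hypotensive event. No event reaches Grade 4, and there are no ECG or hip findings.

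| Pair | Hypotension bullet | Two related Grade 3 or higher | Cohort review |
|---|---|---|---|
| A + A | met | not met | yes |
| B + B | met | met if both are related | yes |
| A + B | not met (one child per branch) | not met (one child) | **no** |

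The A + B result is the same whether or not the Grade 3 event is judged drug-related. Both children in that pair meet the individual criterion.

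The reversal arises when a Grade 3 event takes the place of the Grade 2 events. Adding a Grade 3 event to a trigger already met does not undo it. A persistent event that worsens is recorded again (Section 10.3.1.3), so an earlier Grade 2 record may still count.

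**Size.** The protocol states no operating figure for this rule and no per-child rates, so there is nothing to reproduce. The rates below are assumptions.

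Children on BMN 111 per cohort, from the minimum sizes in Section 9.1:

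- Cohort 1: 3 sentinels plus 13 or 14 of 27 randomized, giving 16 or 17.
- Cohorts 2 and 3: 3 sentinels plus 8 or 9 of 17 randomized, giving 11 or 12 each.

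Let pA be the probability that a child has the Grade 2 pattern only, pB the probability of a Grade 3 event, and q = 1 − pA − pB, with children independent.

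- P(two or more qualify) = 1 − qⁿ − n(pA + pB)qⁿ⁻¹
- P(mixed pair only) = n(n − 1)·pA·pB·qⁿ⁻²
- P(review as written) = the first minus the second. With three or more qualifying children, one branch must hold at least two, so the only case missed is exactly one child in each.

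Example with n = 11 and pA = pB = 0.05:

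- Two or more qualify: 1 − 0.9¹¹ − 11(0.1)(0.9¹⁰) = 1 − 0.3138 − 0.3835 = 0.303.
- Mixed pair only: 110 × 0.0025 × 0.9⁹ = 0.107.
- Review as written: 0.303 − 0.107 = 0.196.
- Share missed: 0.107 / 0.303 = 35%.

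| pA / pB | n | Two or more qualify | Review as written | Gap | Share missed |
|---|---|---|---|---|---|
| 5% / 5% | 11 | 0.303 | 0.196 | 0.107 | 35% |
| 5% / 5% | 17 | 0.518 | 0.378 | 0.140 | 27% |
| 2% / 1% | 11 | 0.041 | 0.025 | 0.017 | 40% |
| 2% / 1% | 17 | 0.091 | 0.056 | 0.034 | 38% |
| 1% / 0.5% | 11 | 0.011 | 0.007 | 0.005 | 42% |
| 1% / 0.5% | 17 | 0.026 | 0.016 | 0.011 | 41% |
| 1% / 0.1% | 11 | 0.006 | 0.005 | 0.001 | 16% |
| 1% / 0.1% | 17 | 0.015 | 0.012 | 0.002 | 16% |

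The chance of an unreviewed mixed pair in at least one of three cohorts (n = 17, 11, 11) is 31% at 5%/5%, 6.6% at 2%/1%, 2.0% at 1%/0.5% and 0.4% at 1%/0.1%.

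**The case against.** The strongest reply is that little is lost in practice. The DMC hears of each child and is consulted before re-challenge. It can make recommendations at cohort level, and it reviews all available safety data before a younger cohort opens. Its charter, which is cited but not shown, may allow ad hoc review. This stands as mitigation: awareness is not lost. It does not restore the trigger, because the protocol ties the DMC's cohort recommendations to the pre-specified stopping criteria, and discretion is not a prescribed review.

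Second, the phrase in which the word cohort follows the second count is plainly garbled, and a pooled count may have been intended. That is possible. But the repeated count reads as separate counting, and a garbled safety rule needs correcting under either reading.

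Third, the rates are assumed. Study 111-202 hypotension was mostly Grade 1, and "All reported events of hypotension were transient and resolved without medical intervention", so a 5% Grade 3 rate has no anchor in the protocol. The share missed also depends on the ratio of the two rates: at low rates it tends to 2·pA·pB/(pA + pB)², which is 44% at 2:1 and about 17% at 10:1. For given rates the gap is an upper bound, because a Grade 3 child who also has two Grade 2 events within 7 days counts in the first branch. All of this holds, and it limits the figures without touching the logic.

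**Conclusion.** The concern holds. As written in both places, a mixed pair meets no cohort criterion, although each child meets the individual one and a pair no more severe does trigger the review. The loss is confined to the prescribed cohort-level review. It arises only when each branch holds exactly one child, no event reaches Grade 4, and no second child has a related event of Grade 3 or higher.

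The absolute probability cannot be derived from the protocol. Under the assumed rates it runs from about 0.1 to 14 percentage points per cohort, and the low end fits the reported experience in older subjects better. The conclusion depends on the wording of the rule and on none of these rates. The gap is real, partly mitigated and cheap to close, so it should be corrected.

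**What to change.** In the Synopsis and Section 9.1.2, replace the cohort hypotension bullet with: *any two subjects each meet the individual hypotension criterion (two symptomatic hypotension events of at least Grade 2 within 7 days, or any hypotensive event of at least Grade 3)*. The reference to the individual criterion carries over its treatment-emergent and assessor conditions.

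The count of two and the 7-day window stay, and every existing trigger is kept. The phrase *at least* adds no other trigger. A child with one Grade 2 and one Grade 3 event already qualifies through Grade 3, and a single Grade 4 event already prompts a cohort review by itself. The only change is that mixed pairs count.

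The cost is one sentence in two places, alignment of the DMC charter if it repeats the rule, and possibly one additional DMC review.
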